## **Safety and Monitoring:**

**Assessment of Side Effects:** Peripheral oxyhemoglobin saturation, BP and HR will be measured non-invasively before and 5, 10, , 30, 60, 90 and 120 minutes after oxytocin injection and before and 10, 20, 30, 60, 90 and 120 minutes after the intranasal administration. Subjects will be informed to report any subjective sensations during or after oxytocin administration and will be queried at the same intervals as vital sign monitoring for any subjective sensations. At the end of Study Visit 2 the nasal passages will be inspected for any localized tissue reaction.

**Treatment of Side Effects:** Significant cardiorespiratory side effects include:

- a. Decreased BP with symptoms of hypotension (e.g., dizziness or lightheadedness)
- b. Blood pressure or HR changes >20%
- c. Pulse oximetry less than 94% that does not correct with several deep breaths.

Treatment of BP elevations > 20% of baseline will be treated with labetalol 5-15 mg IV incrementally until BP elevation <20% elevated. Treatment of symptomatic hypotension or BP reductions >20% will be treated with

incremental ephedrine 5-20 mg, IV. Heart rate (HR) reductions or elevations > 20% of baseline will be treated with incremental glycopyrrolate 0.2 mg IV or propranolol 0.2 mg IV, respectively. Peripheral oxyhemoglobin desaturation (< 90) will be treated with supplemental oxygen, nasal cannula, face mask, or non-rebreathing mask depending upon the degree desaturation and the response to therapy.

Regardless of whether any treatment is required, subjects with significant side effects will be monitored more frequently (every 5 min for BP and HR; continuously for POX) until symptoms or signs resolve.

**Serious adverse events:** In addition to treatment, as described above, and timely reporting as required to the DSMC, IRB, and FDA, emergency treatment will be available within the CRU itself. As such, an ACLS-certified health care professional will be on site or within 5 minutes of the CRU during each treatment session, and a crash cart containing medicine and equipment for emergency resuscitation, and an automated external defibrillator will be located on-site.

**Study Stopping Criteria:** Should significant cardiorespiratory or other side effects occur during oxytocin administration, the IV infusion or intranasal self-administration will be stopped and the subject treated as indicated in Treatment of Side Effects. Blood samples will be obtained near the time of oxytocin cessation and according to the sampling intervals of the study once the side effects are successfully treated or resolve.

The study will be stopped if more than 2 individuals exhibit significant cardiorespiratory side effects or after any serious adverse event and future conduct of the study will be determined by recommendations from the DSMC, IRB, and FDA.

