## Additional Objectives

[figure not shown]
1. Describe adverse events with intravenous and i.n. administration

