## Methods and Measures

Equal numbers of adult men and women will be recruited. Sample size will be divided into 3 groups; young (18-39-year-old) middle (40 – 59-year-old) and older (60 – 75-year-old).

Subjects will report to the CTSI Clinical Research Unit (CRU) for two visits, separated by at least 5 days. On study visit one informed consent will be obtained and eligibility verified. Then two intravenous (IV) catheters will be inserted, one in each forearm, with one for drug infusion and the other for blood sampling. After baseline measures, subjects will receive oxytocin (Pitocin®), 14  $\mu$ g (8.2 IU) over 30 minutes. This dose and infusion duration were chosen based on previous studies showing no adverse events in 10 volunteers and our preliminary PK model which predicts that plasma oxytocin concentrations will be above the limit of detection (1 pg/ml) at 120 min. Venous blood samples (5 ml) will be obtained at 2, 5, 10, 20, 30, 40, 50, 65, 90, and 120 minutes after the initiation of oxytocin administration for oxytocin assay.

On study visit 2, one IV catheter will be placed for blood sampling. After baseline measures, subjects will receive 102  $\mu$ g (60 IU) intranasal oxytocin (Tonix-1900, Tonix Pharmaceuticals, Chatham, NJ). Venous blood samples (5 ml) will be obtained at 1, 2, 5, 7, 10, 15, 20, 25, 35, 45, and 60 minutes after the initiation of the oxytocin administration for oxytocin assay. See graph 3 for rationale for the times of sampling.

**Figure 2. A)** PK modeled OXT concentrations in preliminary data compared with published reports. **B)** Fraction of targeted concentration using TCI. 95% prediction intervals from LC/MS or ELISA assays of duplicate samples (n=11).

We will abandon an individual participant's study and schedule another participant should we be unable to successfully place the intravenous catheters.

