### **Exclusion Criteria**

1. Hypersensitivity, allergy, or significant reaction to any ingredient of Pitocin®
2. Any disease, diagnosis, or condition (medical or surgical) that, in the opinion of the Principal Investigator, would place the subject at increased risk (active gynecologic disease in which increased tone would be detrimental e.g., uterine fibroids with ongoing bleeding), compromise the subject's compliance with study procedures, or compromise the quality of the data
3. Women who are pregnant (positive result for urine pregnancy test at visit 1), women who are currently nursing or lactating, women that have been pregnant within 2 years
4. Subjects with neuropathy, chronic pain (being treated on a daily basis), diabetes mellitus, or taking benzodiazepines or pain medications on a daily basis.
5. Subjects with current or history of ventricular tachycardia, atrial fibrillation or prolonged QT interval.
6. Subjects with past or current history of hyponatremia or at risk for hyponatremia; anyone taking thiazide diuretics, loop diuretics, combination diuretics, lithium, carbamazepine, enalapril, Ramipril, celecoxib, temazepam, gliclazide, glimepiride, glibenclamide, glipizide, omeprazole, pantoprazole, desmopressin, SSRI's, MAOI, or the recreational drug ecstasy.
7. Subjects with a known latex allergy.
8. History of chronic nasal obstruction or local pathology in nostril pathway which, in the opinion of the investigator, would prevent appropriate nasal administration of the study drug.
9. Use of OTC nasal products (ie. Saline spray, Neti-Pot, etc.) or intranasal corticosteroid medications during the study.

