## **Interventions and Interactions**

**Study Visit 1:** The participant will report to the Clinical Research Unit (CRU) of the Wake Forest Clinical Translational Science Institute (CTSI), in the morning after having had nothing to eat or drink since midnight. The participant will review and sign the Informed Consent. After informed consent is adequately obtained, a detailed medical history will be obtained from the participant, female participants will have a urine pregnancy test performed to determine pregnancy status. Vital signs to include blood pressure (BP), heart rate (HR), respiratory rate (Resp) and peripheral oxygen saturation (POX) will be measured and recorded along with height and weight.

Once eligibility has been determined; baseline vital signs (BP, HR, Resp, POX) will be obtained for a baseline measurement and then at the following intervals after the infusion has been initiated; 5, 10, 30, 60, 90 and 120 minutes. Two intravenous catheters will be inserted, one in each arm, and baseline measurements will be obtained. Then 14 µg (8.2 IU) oxytocin (Pitocin®), obtained from the research pharmacy, will be infused over 30 min through one of the catheters. Blood (5 ml) will be sampled from the other catheter at 2, 5, 10, 20, 30, 40, 50, 65, 90, and 120 minutes after the initiation of oxytocin, placed on ice, plasma separated in a refrigerated centrifuge, and stored at -80°C until analyzed for oxytocin concentration. The study will not be blinded. The intravenous catheters will be removed after all data collection and the subject discharged from the CRU. The duration for study visit 2 will be approximately 3.5 hours.

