## **Study Visit 2**

On the second visit, the participant will report to the CRU, in the morning after having had nothing to eat or drink since midnight. Baseline vital signs (BP, HR, Resp, POX) will be obtained for a baseline measurement and then at the following intervals after the intranasal oxytocin: 10, 20, 30, 60, 90 and 120 minutes. One intravenous catheter will be inserted. Oxytocin, 102 µg (Tonix-1900, Tonix Pharmaceuticals, Chatham, NJ), obtained from the research pharmacy, will be self-administered in the nasal passages as one metered spray in each nostril followed in 5 min by a second metered spray in each nostril. Blood (5 ml) will be sampled from the IV catheter at 1, 2, 5, 7, 10, 15, 20, 25, 35, 45, and 60 minutes after the initiation of the oxytocin administration, placed on ice, plasma separated in a refrigerated centrifuge, and stored at -80°C until analyzed for oxytocin concentration. The intravenous catheter will be removed after all data collection and the subject discharged from the CRU. The duration for study visit 2 will be approximately 3 hours.

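### The nasal passages are inspected only after the sprays, so mild pre-existing changes cannot be reliably separated from a local reaction

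*Combined protocol and SAP*

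**What the plan says.** The protocol has one additional objective: "Describe adverse events with intravenous and i.n. administration". For the intranasal route, the local part of that objective rests on one sentence under Safety and Monitoring (Assessment of Side Effects): "At the end of Study Visit 2 the nasal passages will be inspected for any localized tissue reaction".

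The procedures listed before the sprays are these:

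- **Visit 1** (Interventions and Interactions): "a detailed medical history will be obtained from the participant, female participants will have a urine pregnancy test performed", followed by vital signs, height and weight. No nasal examination is listed.
- **Visit 2** (Study Visit 2): "Baseline vital signs (BP, HR, Resp, POX) will be obtained for a baseline measurement", and one intravenous catheter is placed. The subject then self-administers one spray per nostril and repeats this 5 minutes later.
- **Methods and Measures**, on visit 2: "After baseline measures, subjects will receive 102" µg of intranasal oxytocin. The section does not say what the baseline measures are.

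Two exclusion criteria concern the nose. Item 8 is "History of chronic nasal obstruction or local pathology in nostril pathway which, in the opinion of the investigator, would prevent appropriate nasal administration". Item 9 is "Use of OTC nasal products (ie. Saline spray, Neti-Pot, etc.) or intranasal corticosteroid medications during the study".

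**The concern.** A reaction is a change, and one observation made after exposure cannot show change. Someone following the protocol as written would first look into the nostrils at the end of visit 2, after four sprays. Redness, crusting or a small septal abrasion seen then might have been caused by the product or might have been there that morning, and the record would not show which.

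In a placebo-controlled study, the background frequency in the control arm would put such findings in context. Here every subject gets the product unblinded, so nothing outside the subject can play that part. At stake is how far the description of local tolerability of the intranasal product can be trusted. Local tissue reaction is a route-specific finding, and this inspection is the only objective local assessment in the plan.

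**Working it through.** No arithmetic applies. The point concerns the timing of one assessment and does not depend on alpha, power, effect size or sample size. The check was to read every section that mentions the nose, intranasal dosing, baseline, screening or examination, and to compare what is observed before and after dosing.

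| Assessment | Before dosing | After dosing |
|---|---|---|
| BP, HR and oxygen saturation, visit 1 | Yes | Yes, 5 to 120 min |
| BP, HR and oxygen saturation, visit 2 | Yes | Yes, 10 to 120 min |
| Subjective sensations, visit 2 | At the vital-sign times, which on a natural reading include the pre-dose one | Yes |
| Nasal inspection, visit 1 | None listed | None listed |
| Nasal inspection, visit 2 | None listed | Once, at the end of the visit |

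1. **Count.** The documents specify 0 nasal inspections before the sprays and 1 after.

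2. **Contrast within one paragraph.** Assessment of Side Effects explicitly requires saturation, blood pressure and heart rate before and after each administration. The nasal assessment, in the same paragraph, has no such pair, and no reason is given.

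3. **Could the undefined baseline measures include it?** Only Study Visit 2 gives them content, and it names vital signs alone. A site working from the text would have no instruction to inspect.

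4. **Does exclusion 8 supply a baseline?** It covers chronic obstruction or local pathology that would prevent proper nasal administration. Mild redness, crusting or an abrasion would not prevent spraying, so subjects with these remain eligible. They are also the findings most easily mistaken for a reaction. The criterion names no inspection as its basis. The listed source is the visit 1 history ("a detailed medical history will be obtained from the participant"), taken at least 5 days before the sprays, and no maximum interval is set.

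5. **Does exclusion 9 supply one?** It bars products that could irritate or alter the mucosa during the study. It does not record what the mucosa looks like.

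6. **Is there another comparator?** There is no placebo spray, the study is not blinded, and the nose is not inspected on the intravenous occasion either. Only the subject's own pre-dose state is left, and it is not recorded.

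**The case against.** The strongest case on the other side is that other safeguards already do much of this work. Exclusions 8 and 9 remove the more obvious nasal problems. Symptom queries are tied to the vital-sign times, so a subject with congestion or soreness could report it before dosing. Daily contact for one week gives further adverse-event information. The protocol does not say how the investigator forms the opinion required by exclusion 8, so a look into the nose at screening is neither required nor ruled out. The stakes are also low: there is one dosing occasion, the objective is descriptive, and no hypothesis, comparison or count-based stopping threshold uses nasal findings.

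Most of this stands, and it limits the point. It would be too strong to say that a reaction can never be told from a pre-existing finding. What remains is that none of these safeguards records the appearance of the mucosa before the sprays, and a mild change without symptoms would pass through all of them.

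A reader might be tempted to go further in three ways.

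- **Bioavailability.** One might infer that an unnoticed inflamed or obstructed nostril would distort the bioavailability estimate. The documents give no figure linking nasal state to absorption and no frequency for such a state. The Analytical Plan already expects high inter-subject variability in absorption, and nasal status is not a listed covariate. This is speculation.
- **A count of misattributed subjects.** One could multiply the 24 evaluable subjects by an assumed prevalence of pre-existing changes. The documents give no prevalence, and the product would also assume that every such change is attributed to the drug.
- **Re-applying exclusion 8 at visit 2.** This does not follow from the missing baseline. It could lose a subject who has already received the intravenous infusion, and with that subject one of the within-subject pairs. It would also be an eligibility and dosing decision, which is outside this point.

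**Conclusion.** The point holds, and it is minor. As written, the plan observes the nasal mucosa once, after exposure, with no recorded pre-dose state and no control group. Mild pre-existing changes that do not prevent spraying therefore cannot be reliably separated from a local reaction when adverse events are described. The effect is limited to the additional safety objective; the documents do not support extending it to the primary pharmacokinetic outcome.

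No numerical size can be given, because the documents say nothing on how often such changes occur in this population. The conclusion rests on two assumptions: that sites do what the text lists and no more, and that some eligible subjects may have a mild visible change on the day. If an inspection before the sprays is in fact intended as part of the baseline measures, the remaining defect is that the protocol does not say so.

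**What to change.** In Study Visit 2, add an inspection of both nostrils before the first spray, by the same method and on the same form as the end-of-visit inspection. Name it in Methods and Measures as one of the visit 2 baseline measures, so that the two sections agree. Since the protocol describes neither a method nor a form for the existing inspection, set down one that serves both time points. Under Safety and Monitoring, state that findings which are new or worse than the pre-spray inspection are reported as local reactions.

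The cost is a brief extra check and one form line for each subject, of whom there are up to 30. The change adds a measurement and leaves dose, eligibility and treatment as they are. It has to be made before subjects attend visit 2, because a pre-dose observation cannot be recovered once the sprays have been given.

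### No scheduled safety check falls between 10 and 30 min of the infusion or between the two intranasal spray pairs, so in those windows the rule to stop administration rests on spontaneous symptom reports; check times also differ by route

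*Combined protocol and SAP*

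**What the plan says.** The protocol has a rule for stopping administration in the individual subject (Study Stopping Criteria): "Should significant cardiorespiratory or other side effects occur during oxytocin administration, the IV infusion or intranasal self-administration will be stopped". A study-level rule in the same section stops the trial if more than 2 individuals have significant cardiorespiratory side effects, or after any serious adverse event.

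Safety and Monitoring lists three significant cardiorespiratory effects: (a) a fall in blood pressure with symptoms, (b) a change in blood pressure or heart rate of more than 20%, and (c) oximetry below 94% that deep breaths do not correct. Item (b) needs no symptom, and all three involve a measurement.

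The check times are:

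- Visit 1, where the dose "will be infused over 30 min through one of the catheters": vital signs "at the following intervals after the infusion has been initiated; 5, 10, 30, 60, 90 and 120 minutes".
- Visit 2, where one spray per nostril is "followed in 5 min by a second metered spray in each nostril": vital signs "at the following intervals after the intranasal oxytocin: 10, 20, 30, 60, 90 and 120 minutes".
- Symptoms at both visits: subjects are "queried at the same intervals as vital sign monitoring for any subjective sensations". They are also told to report sensations on their own initiative, during or after dosing.

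Monitoring every 5 min, with continuous oximetry, is provided only for a subject in whom a significant side effect has already been found. Describing adverse events by both routes is the one item under Additional Objectives.

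**The concern.** A rule that stops dosing during administration needs information that arrives during administration. The rule's cardiorespiratory triggers are mostly measured signs, and the symptom query is tied to the same clock as the measurements. A long interval without a scheduled check is therefore an interval in which the rule has only volunteered complaints to work on.

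Two things are at stake. The first is safety: a sign that the plan itself calls significant could be present while the rest of the dose is given. If it resolves before the next reading, it is also never counted toward the rule of more than 2 individuals. The second is description: if the two routes are queried at different times, a brief early effect may be recorded more readily after one route than the other. Brief effects are plausible here, because the Background reports transient headache and flushing when a 17 µg dose was given over 1 min.

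**Working it through.** The plan states no figure to reproduce, so the check sets the scheduled times against the dosing windows.

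**Inputs**

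- Infusion: 14 µg over 30 min (Methods and Measures; Study Visit 1).
- Infusion checks: 5, 10, 30, 60, 90 and 120 min from the start (Study Visit 1).
- Intranasal dose: 102 µg as two spray pairs 5 min apart (Study Visit 2).
- Intranasal checks: 10, 20, 30, 60, 90 and 120 min (Study Visit 2).
- Assumptions: constant infusion rate; equal sprays.

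**Infusion**

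| Interval between checks | Length | Share of infusion | Dose given |
|---|---|---|---|
| 0 to 5 min | 5 min | 5/30 = 17% | 14 × 5/30 = 2.3 µg |
| 5 to 10 min | 5 min | 5/30 = 17% | 14 × 5/30 = 2.3 µg |
| 10 to 30 min | 20 min | 20/30 = 67% | 14 × 20/30 = 9.3 µg |

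The 30-min reading coincides with the end of the infusion, so it cannot shorten it. The scheduled checks able to trigger a stop are those at 5 and 10 min.

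**Intranasal**

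The plan does not say whether the vital-sign clock starts at the first or the second spray pair. Blood sampling at the same visit is explicitly timed from the start of administration.

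- Clock from the first pair: the first check is at 10 min, which is 5 min after the second pair.
- Clock from the second pair: the first check is at 5 + 10 = 15 min from the first pair.

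Either way, no scheduled post-dose check precedes the second pair. That pair is 2 of 4 sprays, or 102 × 2/4 = 51 µg of nominal dose.

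**Comparison of the two schedules**

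- Clock from the first pair: five of the six post-dose times agree (10, 30, 60, 90 and 120 min). The 5-min check is intravenous only and the 20-min check is intranasal only.
- Clock from the second pair: the intranasal times from first dose become 15, 25, 35, 65, 95 and 125 min, and none matches an infusion time.

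**Staff contact in the gaps**

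Blood is drawn at 20 min of the infusion and at 1, 2 and 5 min of the intranasal visit. No vital-sign reading or symptom query is written for those draws.

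**The case against.** The strongest reply is that the rule has other ways to act. It covers other side effects as well as cardiorespiratory ones, and subjects are told to report sensations at any time. Infusion readings exist at 5 and 10 min, and someone is at the bedside for blood draws inside both gaps. All of this stands. A reader might infer from the gaps that the stop rule cannot work at all, and the documents do not support that. What remains is narrower: a symptomless change arising inside a gap.

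The expected risk is also said to be low. Methods and Measures cites no adverse events in 10 volunteers. The simulation in Figure 3 assumes 1% intranasal bioavailability, so the second pair would add about 51 × 0.01 = 0.5 µg systemically. These points lower the likely consequence but do not close the gap. Zero events in 10 subjects still has an exact one-sided 95% upper limit of 1 − 0.05^(1/10) = 26%. The 1% is an assumption about the quantity that the trial is meant to estimate. The plan also applies its stop rule to self-administration whatever the expected exposure.

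On ascertainment, the objective is descriptive and no test between routes is planned. A 10-min query can also pick up a sensation felt at 5 min, and subjects are contacted daily for a week. A reader might infer that the comparison of routes is biased beyond use. The documents support only a modest limit on what can be said about early, brief events.

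Finally, the infusion times under Safety and Monitoring contain an empty slot between 10 and 30 min. It may be a dropped time or an artefact of text extraction. Study Visit 1 gives the list without a slot, so the gap stands in the current text.

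**Conclusion.** The point holds in a limited form. The written schedule leaves 20 of 30 min of the infusion (67%; 9.3 of 14 µg at a constant rate) and the whole interval between spray pairs without a scheduled reading or query. In those windows the stop rule depends on spontaneous reports and cannot detect a symptomless change in blood pressure, heart rate or saturation. For the intranasal route, no scheduled post-dose check can trigger the stop at all. A change that persists would still be recorded at the next check and counted toward the study-level rule; one that resolves sooner would be missed.

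The difference between routes is a lesser matter. It is one time point per route if the intranasal clock starts at the first pair, and all times are offset if it starts at the second.

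The result rests on the stated times, a constant infusion rate and equal sprays. It does not rest on plasma concentrations. A reader might want to express the infusion gap as a rise in concentration using the Table 1 parameters, but the table gives no units. Assuming L and L/min, the 17 µg, 30-min target-controlled infusion in the Background would reach 17 / [10.2 + 0.98 × 30 + 7.1 × (1 − e^(−0.21 × 30/7.1))] = 17/43.8 = 0.388 µg/L, about 388 pg/ml. The Background gives 80 pg/ml, so absolute concentrations computed this way are not reliable.

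**What to change.** The sponsor should reconcile the check times in Study Visit 1, Study Visit 2 and Safety and Monitoring with the rule in Study Stopping Criteria, so that scheduled checks cover the administration windows. The protocol should also:

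- state whether intranasal vital signs and queries are timed from the first or the second spray pair;
- collect vital signs and symptom queries at the same times from the start of dosing at both visits;
- resolve the empty slot in the infusion times under Safety and Monitoring.

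The exact schedule is for the sponsor to set, and this point asks for no change to thresholds or treatments. The cost is an edit to the protocol text and about one extra non-invasive reading and query per visit, since staff already draw blood at 20 min of the infusion and at 5 min of the intranasal visit.

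### As written, one asymptomatic blood pressure or heart-rate change above 20% calls for an IV drug, with no repeat reading required, even when both values are within the eligible range

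*Combined protocol and SAP*

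**What the plan says.** All the wording is in the combined protocol and SAP, Safety and Monitoring.

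**Definition (Treatment of Side Effects).** There are three items. Item a is a fall in blood pressure accompanied by symptoms. Item b is "Blood pressure or HR changes >20" per cent. Item c is "Pulse oximetry less than 94% that does not correct with several deep breaths".

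**Treatment.** For rises in pressure: "Treatment of BP elevations > 20% of baseline will be treated with labetalol 5-15 mg IV incrementally". For falls, ephedrine is given for symptomatic hypotension or, as an alternative condition, for any reduction above 20%. For heart rate: "reductions or elevations > 20% of baseline will be treated with incremental glycopyrrolate 0.2 mg IV or propranolol 0.2 mg IV, respectively".

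**Follow-up.** "Regardless of whether any treatment is required, subjects with significant side effects will be monitored more frequently (every 5 min for BP and HR", with oximetry continuous, until the event resolves.

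**Stopping (Study Stopping Criteria).** If a significant effect occurs during dosing, "the IV infusion or intranasal self-administration will be stopped and the subject treated as indicated in Treatment of Side Effects". At study level: "The study will be stopped if more than 2 individuals exhibit significant cardiorespiratory side effects", or after any serious adverse event. After that, "future conduct of the study will be determined by recommendations from the DSMC, IRB, and FDA".

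**The concern.** Items a and c each carry a qualifier: symptoms in a, failure to correct in c. Item b has none. Because symptomatic hypotension has its own item, item b must be meant to reach asymptomatic changes, and the treatment sentence for pressure falls confirms this by listing symptoms and a 20% reduction as alternatives. Blood pressure and heart rate vary from reading to reading, so a single value can cross a 20% boundary without any drug effect.

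The main stake is at subject level. These are volunteers who, by the protocol's own account, will not benefit from taking part. One of them could be given an IV beta-blocker, vasopressor or anticholinergic for a single reading that would itself have satisfied the entry criteria. A secondary stake is the study-level count, since each such subject moves the study toward a halt at the third individual.

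**Working it through.** **1. Can item b be met with both values inside the eligible range?** Inclusion Criteria: systolic 100–140, diastolic 60–90, heart rate 45–90 (45–100 for treated hypertensives). Change = follow-up / baseline − 1.

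| Sign | Baseline to follow-up | Change | Drug named |
|---|---|---|---|
| Heart rate | 45 to 55 | 55/45 − 1 = +22.2% | propranolol |
| Heart rate | 75 to 59 | 59/75 − 1 = −21.3% | glycopyrrolate |
| Systolic | 100 to 121 | 121/100 − 1 = +21.0% | labetalol |
| Systolic | 135 to 107 | 107/135 − 1 = −20.7% | ephedrine |
| Diastolic, if it counts | 62 to 75 | 75/62 − 1 = +21.0% | labetalol |

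Yes, in both directions. The protocol does not say which blood pressure component counts.

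**2. Is there a confirmation step?** The 5-minute readings apply to subjects who already have a significant side effect. They follow the classification and do not test it.

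**3. How often could it arise?** There are 6 post-dose checks at each visit, so 12 per subject. Of these, only the 5- and 10-minute checks at visit 1, and arguably the 30-minute check at the end of the infusion, can stop dosing. At visit 2 the sprays are at 0 and 5 minutes and the first check is at 10.

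**4. Study-level count.** The plan states no expected event rate or halt probability, so there is no figure to reproduce. If a share p of subjects has a counted event, then

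P(stop) = 1 − (1−p)^n − n·p·(1−p)^(n−1) − [n(n−1)/2]·p²·(1−p)^(n−2).

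For n = 24 and p = 5%: 1 − 0.292 − 0.369 − 0.223 = 11.6%.

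| Assumed p | n = 24 | n = 30 |
|---|---|---|
| 2% | 1.2% | 2.2% |
| 5% | 11.6% | 18.8% |
| 10% | 43.6% | 58.9% |
| 20% | 88.5% | 95.6% |

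Methods and Measures cites no adverse events in 10 earlier volunteers. That does not fix p: the one-sided 95% upper limit for 0 of 10 is 1 − 0.05^(1/10) = 25.9%, and the event definition used there is not given.

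**5. Dependence on unstated variability.** This is a simulation with no drug effect and n = 24. It assumes heart rate, systolic and diastolic all count and are independent of each other, with 12 readings per sign and exchangeable correlation within a visit.

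| Assumed CV | Correlation 0 | 0.3 | 0.5 | 0.7 |
|---|---|---|---|---|
| 3% | about 0 | about 0 | about 0 | about 0 |
| 5% | 76% | 6% | <0.1% | about 0 |
| 6% | >99.9% | 79% | 9% | about 0 |
| 8% | >99.9% | >99.9% | >99% | 21% |

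The two axes are nearly one unknown, roughly CV × √(1 − correlation). For example, 6% × √0.5 = 4.2%. Nothing in the documents selects a cell.

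**6. What confirmation would trade.** These figures are at CV 5% with independent readings. If confirmation also governed the count, the 76% above would fall to 1.4%. For one sign at one visit, detection of a true +30% change lasting all six readings goes from 99.5% to 97%. Detection of a +25% change lasting one reading and its repeat goes from 72% to 58%.

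**The case against.** The strongest reply is that a sensitive trigger is a legitimate choice in healthy volunteers. The study stop is a pause, and the oversight bodies can judge at that point whether the events were noise. This stands for the study-level count: preferring fewer pauses is a choice between sensitivity and specificity, and by the figures above confirmation does lose some brief true changes. It is not for a statistical reviewer to settle.

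Second, the text may allow discretion. The follow-up sentence contemplates a significant side effect that needs no treatment, the term side effect may imply attribution to oxytocin, and incremental dosing implies re-measurement. Only part of this stands. Re-measurement guides later increments, not the first. No attribution step is given. The phrase about treatment has a natural use elsewhere: saturation below 94% that does not correct is a significant side effect, but oxygen is specified only below 90%. For item b, staff have three directive treatment sentences and no rule for withholding a drug.

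Third, a bare confirmation rule could harm. It might delay treatment of a severe asymptomatic fall, or discard a true oxytocin effect that resolved because dosing was stopped. Both objections stand, and the fix below is framed to meet them.

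A reader might also infer that the rule will probably halt the study without cause. The documents do not support that, because they give no within-person variability and the answer moves from about zero to near certain with the assumption.

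**Conclusion.** The gap is real and lies in the wording: item b has no symptom or persistence condition, and the treatment sentences attach IV drugs to it. Values within the eligible range are enough to trigger it. This conclusion rests on the text and simple ratios, and does not depend on the simulated probabilities.

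Its size is modest. It concerns avoidable IV treatment of an asymptomatic volunteer, at a frequency the documents do not allow anyone to estimate. A halt would be temporary if the oversight bodies so advise. A reader might infer damage to the pharmacokinetic or bioavailability estimates, but none is shown, and few scheduled readings can interrupt dosing at all. This is a cheap improvement to consider and does not threaten the study's objective. Confidence is medium, because site practice may already include a repeat reading that the protocol does not state.

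**What to change.** In Treatment of Side Effects:

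- Keep a change above 20% as the trigger for closer monitoring and for stopping the individual's dosing.
- For an asymptomatic blood pressure or heart-rate change, require a repeat reading, either immediate or at the 5-minute check already specified, that is still above 20% in the same direction before any IV drug is given.
- Treat at once if there are symptoms, or if the value crosses an absolute limit set in advance by the investigator and the DSMC.
- State which blood pressure component counts.

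In Study Stopping Criteria, ask the DSMC to decide whether unconfirmed changes count toward the third individual. If it adopts confirmation there, any change that led to dosing being stopped should still count even if it then resolves. Unconfirmed changes should be listed in the quarterly cumulative report. Items a and c and the stop after any serious adverse event stay as they are.

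The cost is a few sentences of wording, agreement on absolute limits, and reporting the protocol change to the IRB, DSMC and FDA as each requires. No additional subjects are needed. The downside is a few minutes' delay before treating a mild asymptomatic change. If the DSMC also applies confirmation to the count, there is the loss of sensitivity to brief changes shown in the working.
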